Subjects with prolactinomas who are resistant to dopamine agonist therapy who manifest continued tumor size growth while on a dopamine agonist, unless intolerant of adequate doses of a dopamine agonist.

Subjects with malignant pituitary tumors will be eligible for the malignant pituitary tumor arm of the study regardless of existing visual deficits.

Exclusion criteria: Children will be excluded. If subjects have preexisting visual field deficits, they will be monitored on more frequent basis. Patients will also be excluded if they have left ventricular ejection fraction less than 50 %, moderate to severe hepatic impairment (see below for specifics), active hepatitis, HIV positivity, concurrent cancers, life expectancy less than one year, and pregnancy. Pregnant patients will be excluded. Childbearing age women will be required to use

contraception. Patients who become pregnant during the study should discontinue the study immediately.

Withdrawal of Subjects:

Monitoring for adverse effects: Prior to initiating therapy, patients will undergo an echocardiogram and ECG to evaluate the ejection fraction, and the echocardiogram will be repeated every 8 weeks (Visit 3, 5, and 7) and on visit 8. Patients will also undergo ophthalmic testing at visits 1, 4, and 7. Patients with pre-existing stable visual field compromise prior to enrollment will undergo visual field testing at visits 1, 2, and 3, and if stable, then they will proceed with visual field testing every three months for the duration of the study. Patients will be evaluated for adverse effects monthly with physical examinations, chemistry and hematology panels, and ECGs. Adverse events will be graded by the NCI-CTC and include: anorexia, decreased ejection fraction, interstitial lung disease/pneumonitis, diarrhea, nausea, vomiting, hepatotoxicity, rash, and fatigue. Lapatinib will be discontinued in those who developed decreased ejection fraction, who develop pulmonary symptoms, retinal toxicity, worsening of visual fields, and those with toxicity greater than or equal to Grade 2 on the NCI-CTC. [name], from Oncology department at Cedars-Sinai Medical Center, will assist us in monitoring patients for adverse events.

If at any time a patient demonstrates compromise of his visual fields, dilated retinal exam or tumor growth on MRI, he will be withdrawn from the study and referred for surgery.

Section 6.0 Treatment of Subjects

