who received lapatinib and 7% in those on placebo. Risks of adverse events are not additive or cumulative. SAEs were reported in 6% of those on lapatinib compared to 5% on placebo. Cardiac events including left ventricular ejection fraction decreases were reported in approximately 1% of patients and most have partial or full recovery. Symptomatic decreases in ejection fraction were observed in approximately 0.3% of patients on lapatinib. Interstitial lung disease is observed in 0.2% of patients. Hepatotoxicity has been observed in <1% of patients. Grade 3 and 4 diarrhea occurs in <10% of patients. Nausea may be seen in 18% of patients and rash in 29% (Investigators' Brochure).

2. Prior to initiating therapy, patients will undergo an echocardiogram and ECG to evaluate the ejection fraction, and the echocardiogram will be repeated every 8 weeks and on visit. Patients will be evaluated for adverse effects monthly with physical examinations, chemistry and hematology panels, and ECGs. Adverse events will be graded by the NCI-CTC. Common adverse events include: hand-foot syndrome, rash, diarrhea, indigestion, nausea, vomiting, anorexia, anemia, low platelets, abnormal liver tests (ALT (SGPT) level raised, AST/SGOT level raised, hyperbilirubinemia, backache, pain in limb, insomnia, fatigue, and shortness of breath. Rare but serious events include: heart failure (depression of left ventricular systolic function), abnormal heart beat (prolonged QT interval), liver damage (hepatotoxicity), and lung problems (interstitial lung disease/pneumonitis). Lapatinib will be discontinued in those who developed decreased ejection fraction, who develop pulmonary symptoms. Those subjects with toxicity less than or equal to Grade 2 on the NCI-CTC will have their dose held and resumed when the toxicity has resolved. Those subjects with toxicity equal to Grade 3 on the NCI-CTC will have their dose held and resumed at a fifty percent dose reduction when the toxicity has resolved. Those subjects with toxicity equal to Grade 4 on the NCI-CTC will be discontinued on the study drug. [name], from Oncology department at Cedars-Sinai Medical Center, will assist us in monitoring patients for adverse events.
3. If at any time a patient demonstrates a worsening of their visual fields or tumor growth on MRI, they will be withdrawn from the study and referred for surgery.

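### Sections 5.0 and 8.0 give different eye stopping rules: only Section 5.0 has a retinal trigger, and its visual-field wording leaves stable baseline loss ambiguous

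*Combined protocol and SAP*

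**What the plan says.** Section 5.0 (Selection and Withdrawal of Subjects) contains two eye rules.

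- The drug-stopping sentence lists patients "who develop pulmonary symptoms, retinal toxicity, worsening of visual fields" among those whose lapatinib is discontinued.
- The withdrawal sentence reads "If at any time a patient demonstrates compromise of his visual fields, dilated retinal exam or tumor growth on MRI, he will be withdrawn" and sends such patients for surgery.

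The same section admits patients with visual loss. For all subjects, "If subjects have preexisting visual field deficits, they will be monitored on more frequent basis". For the malignant arm, "Subjects with malignant pituitary tumors will be eligible for the malignant pituitary tumor arm of the study regardless of existing visual deficits". It then sets the follow-up: "Patients with pre-existing stable visual field compromise prior to enrollment will undergo visual field testing at visits 1, 2, and 3". Those who remain stable carry on with three-monthly testing.

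Section 8.0 (Assessment of Safety) states the rules again. Item 2 says "Lapatinib will be discontinued in those who developed decreased ejection fraction, who develop pulmonary symptoms" and adds nothing on the eye. It then handles toxicity by grade: up to Grade 2, hold and resume on resolution; Grade 3, hold and resume on resolution at a reduced dose; Grade 4, discontinue. Item 3 applies when a patient "demonstrates a worsening of their visual fields or tumor growth on MRI, they will be withdrawn from the study". It has no retinal item.

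**The concern.** A stopping rule that appears twice should give the same answer both times, and these two do not. A retinal finding stops the drug and ends participation under Section 5.0. Under Section 8.0 it can lead to a pause and a restart. For visual fields, the withdrawal sentence in Section 5.0 uses one word both for a state that patients may enter with and for a state that removes them.

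Two things are at stake. The first is safety: whether a patient with a retinal event goes back on drug could depend on which section a site follows. The second is the endpoint. Section 9.0 makes the change from baseline to 6 months the primary hypothesis, with 24 prolactinoma and 6 nonfunctioning subjects planned. A patient withdrawn early has no stated follow-up MRI, and Section 9.0 does not say how withdrawn subjects are counted. The liver rules in Section 8.0, by contrast, keep permanently discontinued subjects in the study assessments.

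**Working it through.** The plan states no figure on this point, so the check is to apply each rule as written to the same two patients.

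| Rule | A: new retinal toxicity, fields unchanged, no tumour growth | B: stable baseline field loss, unchanged on study |
|---|---|---|
| Section 5.0, drug-stopping sentence | Stop drug | Not met (*worsening*) |
| Section 5.0, withdrawal sentence | Withdraw and refer for surgery | Met if read literally (*compromise*); not met if progression was meant |
| Section 8.0 item 2 | Not named; Grade 1–2 hold and resume, Grade 3 hold and resume reduced, Grade 4 stop | No visual-field item |
| Section 8.0 item 3 | Not met | Not met (*worsening*) |

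**Patient A.** The two sections disagree for Grades 1 to 3, and no interpretation is needed to see it. Table 1 in Section 8.0 adds a further answer for lapatinib-related non-hematological events of Grade 1 or 2: continue at full dose.

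**Is this only the general grade conflict?** Partly. Section 5.0 also stops the drug for any toxicity of Grade 2 or above, which already clashes with Section 8.0 item 2. But a Grade 1 retinal event is stopped in Section 5.0 by the retinal wording alone. Settling the grade rules would therefore not by itself settle the retinal question.

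**Can the case arise?** Yes. The visit list and flowsheet schedule dilated retinal exams at baseline and at Visits 4 and 7.

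**Patient B.** The disagreement depends on how *compromise* is read. Within Section 5.0 the word describes both the admitted stable state and the withdrawal trigger, and the trigger has no reference to baseline.

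**Surgical referral.** In the Section 5.0 sentence a retinal finding alone leads to referral for surgery, as field loss and tumour growth do. The drug-stopping sentence treats retinal toxicity as a reason to stop lapatinib. The text does not say whether both consequences apply.

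**Link to the 6-month MRI.** Visit 7 holds the retinal exam, the field test and the 6-month MRI together, so a finding there need not cost the MRI. The scheduled tests that could cost it are the Visit 4 retinal exam, the Visit 4 field test and, for those with field deficits, the field tests at Visits 2, 3 and 6. Each prolactinoma patient lost is 1/24 = 4.2% of the sample on which power was computed. The malignant arm has progression-free survival as its primary outcome, so this link does not apply there in the same way.

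**The case against.** The strongest reply is that a sensible reader would not be misled. Section 5.0 lets patients with stable loss proceed and, in its drug-stopping sentence, refers to worsening. In context, then, *compromise* means new or progressive loss, and Section 8.0 item 3 agrees. This largely stands. A reader might infer that the plan withdraws every patient it admits with a field deficit; the documents do not support that. What remains is an undefined trigger in a mandatory rule used at three sites.

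A second reply is that Section 8.0 does not cancel Section 5.0, so a site could apply both, and that Section 8.0 resumes drug only after resolution. Both statements are correct. It would be wrong to say that Section 8.0 orders re-exposure during an active retinal event. But neither section says which prevails, so a site working from Section 8.0 alone has no retinal stopping rule.

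A third reply is that Section 6.0 excludes optic chiasm compression, which may leave few patients with field loss. That may be so, but the plan still schedules extra tests for them, and the retinal conflict applies to all patients.

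A reader might also fault both sections for acting on a single field test, with no size of change and no repeat, and point to the repeat evaluation for asymptomatic LVEF decline. The two sections do not contradict each other here, and whether to require confirmation is a clinical choice. Nor is LVEF a settled model: Section 5.0 and Section 8.0 item 2 stop the drug for decreased ejection fraction with no repeat mentioned.

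**Conclusion.** The point holds as an internal inconsistency. The retinal part rests on the text alone: Section 5.0 has two retinal triggers, and Section 8.0 items 2 and 3 have none. The visual-field part is an ambiguity, with progression the probable intent. The consequence is that the same eye finding could lead to stopping or restarting drug, or to withdrawal or continuation, depending on the site.

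The size cannot be computed. The documents give neither the number of patients with baseline field loss nor a rate of retinal events or of false field changes. A reader might be tempted to assume a 5–10% false-worsening rate per test and compound it over five tests (23–41%) or two (10–19%). Those figures should not be used as the size of the loss. The rate has no source in the documents, the tests would have to be independent, and the count includes Visit 7, where the 6-month MRI is done anyway.

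**What to change.** Reconcile Sections 5.0 and 8.0 into one eye rule, worded identically or stated once and cross-referenced. It should say:

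1. whether a retinal finding is a trigger and, if so, with what consequence (hold, discontinuation of drug, or withdrawal from the study);
2. whether the visual-field trigger refers to change from the patient's baseline;
3. whether surgical referral applies to a retinal finding alone.

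Table 1 should be checked against the result. Which rule is right is for the sponsor and the investigators to decide. The cost is amendment wording and notice to the three sites; settling the wording adds no visit or test.

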Pregnancy Test for pre-menopausal women	X	X	X	X	X	X	X	X

^ Only for subjects with visual field deficits

^^ will be waived if subjects had MRI at outside hospital within 3 months of baseline visit

* Only for subjects with acromegaly from malignant tumors

+Only for subjects with ACTH secreting adenomas from malignant tumors

**Visit 8 is only required if stopping Lapatinib at visit 7. Patients continuing on Lapatinib after visit 7 will be followed by their physician as clinically appropriate.

Section 7.0 Assessment of Efficacy

a. Primary outcome variable.

Primary outcome in nonfunctioning pituitary adenomas: 40% reduction in tumor size in any dimension. Tumor size and volume will be calculated using Open Source OsiriX® Imaging Software for MacOS. MRIs will be performed at baseline and at 3 and 6 months All MRIs will be centrally read by the dedicated pituitary radiologist at CSMC.

Primary outcome in prolactinomas: 40% reduction in tumor size in any dimension.

Primary outcome in malignant pituitary tumors: Progression free survival

b. Secondary outcome variables.

Secondary outcomes in prolactinomas:

(a) achievement of 50% reduction of PRL levels (b) PRL normalization (c) percent reduction in PRL levels (d) percent reduction in tumor volume. Tumor volume will be calculated using Open Source OsiriX® Imaging Software for MacOS. (e) correlation of tumor size and PRL reduction (f) clinical predictors of TKI response, including age, gender, duration of disease, dose and duration of dopamine agonist therapy, baseline PRL, and baseline tumor size.

Secondary outcomes in malignant pituitary tumors: partial response, complete response, mortality, 24 hour urine free cortisol levels for Cushing carcinomas, IGF-1 levels for acromegaly carcinomas

We will correlate ErbB receptor expression with the subjects' clinical response to the study drug. This will be performed through immunohistochemistry staining of pituitary tumor slides from surgery.

Section 8.0 Assessment of Safety

1. *Monitoring for adverse effects (further detailed below):* Data has been collected on over 12000 subjects on combination therapy of lapatinib and other chemotherapies, and over 4000 subjects have been treated with lapatinib monotherapy, with 2347 of those specifically in breast cancer. With monotherapy, majority of AEs were Grade 1 or 2 in severity. The incidence of Grade 3 and Grade 4 events was 21% in those

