Patients should be instructed to notify the investigator if it is determined after completion of the study that they become pregnant either during the treatment phase of the study or within five days after the treatment period.

Whenever possible a pregnancy should be followed to term, any premature termination reported, and the status of the mother and child should be reported to GlaxoSmithKline after delivery.

Section 9.0.

Statistics

Sample size calculation for prolactinomas: Sample size was computed using proportions as standard deviation for tumor reduction on the study drug was unknown. While for the data analysis we will use quantitative analysis using the Hotelling’s T², using binary data for power calculations would be inefficient as this would require a larger sample size. We could not use the quantitative analysis for power calculations, however, as we do not know the variance.

The primary outcome is a reduction in maximal size of resistant tumors. Stabilization is defined as <20% reduction in any dimension on MRI by RECIST criteria. MRIs will be performed at baseline and at 3 and 6 months.

The null hypothesis is H₀: no reduction P<0.20 vs. the alternative hypothesis H_a: P>0.40. This will give an effect size of 0.20 to detect. Exact confidence interval and significance test is obtained from the binomial distribution. The reduction is for resistant prolactinomas (Di Sarno, 2001; Delgrange, 2009). Power is >80%, using one tailed

CSMC Office of Research Compliance

Reference: [ICH E6: Good Clinical Practice: Consolidated Guidance](#)

RECOMMENDED ELEMENTS OF A SCIENTIFIC PROTOCOL
(Noted sections should only be included as applicable to your research)

hypothesis, alpha of 0.10. This gives a target sample size of 24 subjects to achieve this power.

Sample size: use one-sided exact test. $H_0: p = p_0$; $H_A: p > p_0$.

Power	alpha	P_0 : null proportion	P_1 : true proportion	N
80%	0.05	20%	30%	116
80%	0.10	20%	30%	88
80%	0.05	20%	35%	56
80%	0.10	20%	35%	44
80%	0.05	20%	40%	35
80%	0.10	20%	40%	24

Secondary MRI studies will deal with various aspects and location by MRI of these tumors. Secondary PRL statistical studies will also be carried out under secondary outcomes.

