Tumor maximal size will be obtained at baseline, 3 months, 6 months after initiation of treatment. The primary hypothesis is the change from baseline to 6 months. The analysis using maximal resistant tumor size will be carried out for the specified times given above. Initially this will be by descriptive analytic and then by inferential analysis using the test for change between baseline and 6 months and change between baseline and 3 months using rank test. We will also use Hotelling's T^2 to combine both pre-post changes.

This study is in the clinical trials paradigm essentially a Phase IIa trial and thus use of alpha type 1 error is at 10%. This is sanctioned by the biostatistics section of NCI.⁴⁰ We will also analyze the secondary endpoints of Aim 1 according to the above models. Concepts behind analysis for quantitative and binary are the same though the methods are different.

Our overall target sample size is 30 subjects which includes nonfunctioning adenomas and prolactinomas, 15 to be recruited from Cedars Sinai Medical Center and 15 from Johns Hopkins Hospital and Massachusetts General Hospital. We aim to recruit 24 subjects with prolactinomas and 6 nonfunctioning adenomas.

Due to the rarity of pituitary tumors in the general population and even more rare are aggressive pituitary tumors such as we propose to study, it is difficult to do a randomized placebo controlled trial with sufficient sample size numbers to achieve adequate power. By using the subjects as their own controls, we alleviate the issues with recruitment. This is a safety and activity trial to look for a sufficient effect of the drug on tumor growth before proceeding to a larger, randomized placebo controlled trial.

Section 10.0. Quality Control and Quality Assurance

Only samples and data collected with appropriate consent will be used for the proposed analysis. Specimens and data collected under the proof of concept clinical trial of lapatinib will be coded in such a way so that other members of the research team will be unable to ascertain the identity of specific patients. All of our data will be

RECOMMENDED ELEMENTS OF A SCIENTIFIC PROTOCOL
(Noted sections should only be included as applicable to your research)

38

maintained confidentially. Data will be kept in locked file cabinets and in password protected files on computer systems.

Section 11.0 Ethical considerations relating to the trial

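### No rule says how a patient withdrawn for tumour growth at the 3-month MRI enters the 6-month tests, and the default of leaving such patients out leans towards the drug

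*Combined protocol and SAP*

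**What the plan says.** **Withdrawal.** Section 5.0 removes a patient who shows "tumor growth on MRI, he will be withdrawn from the study and referred for surgery". Section 8.0 repeats the rule: "tumor growth on MRI, they will be withdrawn from the study and referred for surgery". Neither states how much growth counts. The one size limit tied to RECIST, in Section 9.0, concerns reduction: "Stabilization is defined as <20% reduction in any dimension on MRI by RECIST criteria".

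**Scans.** MRIs are at baseline, Visit 4 (3 months) and Visit 7 (6 months). The Section 6.0 flowsheet notes that "Visit 8 is only required if stopping Lapatinib at visit 7", and Visit 8 has no MRI. No early-withdrawal visit is described. Section 8.0 requires continued study assessments only after liver-chemistry discontinuation. Section 6.0 describes later data collection only for responders who stay on drug.

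**Analysis.** Sections 4.0 and 7.0 define the primary outcome for prolactinomas and nonfunctioning adenomas as a 40% shrinkage in one dimension. Section 9.0 sizes the prolactinoma cohort on a binary test: "Exact confidence interval and significance test is obtained from the binomial distribution". It then states: "The primary hypothesis is the change from baseline to 6 months". The plan is for "inferential analysis using the test for change between baseline and 6 months and change between baseline and 3 months using rank test", with Hotelling's T² "to combine both pre-post changes". Section 9.0 defines no analysis set and no rule for a missing MRI.

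**The concern.** This is not ordinary dropout. The event that removes a patient before the 6-month scan is the outcome itself, growth on the 3-month scan. If the two scans are positively correlated, those who remain have a more favourable 6-month change than the full cohort, even when the drug does nothing. An off-study MRI obtained later would follow a surgical referral and could show the effect of surgery.

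There is a second, smaller gap. Patients with pre-existing visual-field compromise are tested at Visits 2 and 3, before the first on-drug MRI. One withdrawn then has no post-baseline MRI and no rule.

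Section 9.0 presents the trial as the activity screen before a larger randomised study, so a falsely favourable result would carry forward. Without a rule, the handling of these patients would also be chosen after open-label results are known.

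**Working it through.** **1. The plan's own figure.** Inputs from Section 9.0: null rate 0.20, alternative 0.40, one-sided alpha 0.10, N = 24. The smallest r with P(X ≥ r | 24, 0.20) ≤ 0.10 is r = 8. This gives alpha P(X ≥ 8 | 24, 0.20) = 0.0892 and power P(X ≥ 8 | 24, 0.40) = 0.808. N = 24 reproduces.

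**2. Exact test if completers were the denominator.** Let a share w be withdrawn, all non-responders. Completers M ~ Bin(24, 1 − w), their response probability under the null is 0.20/(1 − w), and r(m) is the 10% critical value at m. Type I error = Σ P(M = m) · P(Bin(m, 0.20/(1 − w)) ≥ r(m)).

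| w | 0.20/(1 − w) | Type I error |
|---|---|---|
| 5% | 0.211 | 9.1% |
| 10% | 0.222 | 10.5% |
| 20% | 0.250 | 16.3% |
| 30% | 0.286 | 24.8% |

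With all 24 counted it is 8.9%.

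**3. Direction of bias at 6 months.** Assumptions, none from the documents (Section 9.0 says the variance is unknown): percent changes are bivariate normal, SD s₃ = 10 or 15 at 3 months and 15 at 6 months, correlation 0.7, and withdrawal if the 3-month change exceeds c. With no true change, the mean 6-month change among those who remain is

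−0.7 × 15 × φ(c/s₃)/Φ(c/s₃).

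For c = 0 this is −10.5 × 0.3989/0.5 = −8.4 points. For c = 10 and s₃ = 15 it is −10.5 × 0.3194/0.7475 = −4.5. It is negative for any positive correlation.

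**4. False success at N = 24, no true change (simulation).** The signed-rank test is one-sided at 10%. T² is a two-sided 10% test, so about 5% is expected towards shrinkage. Pairs are s₃ = 10 / 15; ranges cover both SDs and repeat runs.

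| Growth that triggers withdrawal | Withdrawn | Mean 6-month change in the rest | Rank test | T² towards shrinkage |
|---|---|---|---|---|
| none | 0 | 0 | 10% | 5% |
| >20% | 2% / 9% | −0.6 / −1.9 | 12–23% | 7–15% |
| >10% | 16% / 25% | −3.0 / −4.5 | 35–52% | 32–62% |
| any | 50% / 50% | −8.4 / −8.4 | 78–79% | about 98% |

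Over correlations 0.5–0.9 the rank-test figures are about 12–27%, 25–71% and 53–98%.

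**5. If tumours truly grow (assumed +3% at 3 months, +6% at 6 months; correlation 0.7).** The rank test on those who remain rejects in under 1%, 3–7% and about 32–37% under the three rules. At correlation 0.9 the >10% rule reaches 14%. T² is falsely favourable in about 5–25% at >10% and about 80% at any growth.

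**6. With the growth withdrawals put back.** Carrying forward the triggering MRI's change, the rank test rejects in 2–10% under no change at correlation 0.7. The worst cell (correlation 0.9, SD 10/15, any growth) gives about 13–14%. T² on carried-forward values rejects in up to 33% under no change in that same cell, about 23% of trials being towards shrinkage. A likelihood-based repeated-measures model rejects in 10–12% at correlation 0.7. It suits this problem because withdrawal depends on the 3-month value, which is observed.

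**The case against.** The strongest reply is that the named outcome is binary. A patient withdrawn for growth reads naturally as a non-responder, and with all 24 counted the exact test keeps its level. That stands: a reader might infer that the binomial test is biased as planned, but the plan never says that completers are the denominator. It does not say the opposite either, and Section 9.0 attaches the primary hypothesis to the 6-month change, so the rank test cannot be set aside as secondary.

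A reader might also infer that the plan specifies a completers-only analysis. It does not. A rank test can include these patients once a rule is written; leaving them out is only what happens by default.

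It may also be said that resistant tumours tend to grow, which would offset the bias. For the rank test this is largely right unless the growth rule is strict. For T² it is not, as step 5 shows. Nor can one claim that most prolactinoma patients enter with a growing tumour: Section 5.0 also admits patients intolerant of a dopamine agonist and gives no split.

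Finally, the baseline-to-3-month rank test and growth first seen on the 6-month MRI are unaffected, and the malignant arm uses progression-free survival. All of this limits the point without removing it.

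**Conclusion.** The gap is real and should be fixed before analysis. Two stated rules together remove patients from the 6-month tests because of the outcome, and nothing says how to score them. Confidence is high for the gap and for its direction, which needs only positive correlation between scans.

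Confidence is low for the size. SD, correlation, growth threshold, withdrawal rate and the course of an untreated tumour are all assumed. The 78–79% figure is not an estimate of this trial's error rate: it is the result if any measured growth triggers withdrawal, the true mean change is zero and correlation is 0.7. With a >20% rule and the same assumptions the rank test is at 12–23% against a nominal 10%. The sample size of 24 is correct for its inputs.

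**What to change.** Add the following to Section 9.0, for both the prolactinoma and the nonfunctioning cohorts:

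1. **Binary outcome.** Analyse all treated patients, with all treated as the denominator. Withdrawal for growth or visual fields counts as non-response, as does having no post-baseline MRI for any other reason.
2. **6-month rank test.** Carry forward the change on the MRI that triggered withdrawal, with worst rank as a sensitivity analysis. A patient withdrawn for visual fields with no post-baseline MRI gets the worst rank. Other patients with no post-baseline MRI are reported by number and reason.
3. **Joint analysis.** Do not run Hotelling's T² on the remaining patients only or on carried-forward values. Replace it with one prespecified likelihood-based repeated-measures model of the 3- and 6-month changes in all treated patients, labelled supportive.
4. **Threshold.** The sponsor should state the growth threshold it uses. None is proposed here, and the clinical withdrawal rule is unchanged.

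No extra scans are needed. The cost is rank-test power. With assumed shrinkage of 6% and 9% at 3 and 6 months and correlation 0.7, carry-forward gives 90–94% (>20%), 80–93% (>10%) and 64–88% (any growth), against 94% with no withdrawal. Worst rank as the main analysis would give 87–93%, 52–84% and 4–12%, hence its place as a sensitivity analysis. Each visual-field withdrawal given the worst rank also costs power: 94% falls to 83% with one and 62% with two. Carry-forward is approximate and can exceed 10% when the scans are very highly correlated (step 6).
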